7.3 LOST TO FOLLOW-UP

A participant will be considered lost to follow-up if he or she fails to return for the final scheduled visit and is unable to be contacted by the study site staff. Attempts to contact will occur as below for all missed study visits.

The following actions must be taken if a participant fails to return to the clinic for a required study visit:

- The site will attempt to contact the participant, reschedule the missed visit within ± 3 days for the weekly visits and within ± 2 weeks for monthly visits, and counsel the participant on the importance of maintaining the assigned visit schedule and ascertain if the participant wishes to and/or should continue in the study.

- Before a participant is deemed lost to follow-up, the investigator or designee will make every effort to regain contact with the participant (where possible, 3 telephone calls and, if necessary, a certified letter to the participant's last known mailing address or local equivalent methods). These contact attempts should be documented in the participant's medical record and study file.
- Should the participant continue to be unreachable, he or she will be considered to have withdrawn from the study with a primary reason of lost to follow-up.

8 STUDY ASSESSMENTS AND PROCEDURES

8.1 STUDY PERIOD DEFINITIONS

Baseline & Screening Period

After initial eligibility is determined and informed consent is provided, participants will be assessed against all eligibility criteria over a two-month period. Initial lab results will be compared with repeat lab results obtained within 30 days of the embolization procedure to confirm eligibility. The signed consent form authorizes abstraction of existing data from a patient's medical chart for data collection. Participants will be screened by two physicians, an interventional radiologist, and an internist who specializes in obesity. Screening and baseline visits may be combined if patient and physician schedules will allow. The screening phase begins when the informed consent is fully signed and dated and ends at randomization. The PI may repeat any of the screening tests.

Pre-Procedure Period

This period begins after initial eligibility is determined during the Baseline & Screening Period and ends at randomization.

Procedure Day

This day is scheduled only after all eligibility criteria are satisfied during the previous periods.

Follow-Up Period

This period begins with day 1 post Procedure Day and ends at the final visit at month 12.

Participants will be in the study for up to two years after signing consent and 12 months post embolization. Participants may be followed clinically for up to five years per routine care after the end of the study. For their 12 months of follow up post-procedure, the participants will be asked to come to clinic visits at weeks 1 and 2, and months 1, 3, 6, and 12.

During each clinic visit the following may occur:

- Participants will be evaluated by a study team member, data and home logs will be recorded and collected, will undergo a targeted history and physical exam, and will be asked to fill out any needed questionnaires.
- When attending weight management visits, they will also be evaluated by an internist who specializes in weight management.
- Medication changes will be documented.
- Intensive medical therapy consisting of lifestyle counseling and weight management will be provided to all participants. Diabetic subjects will have their medications managed by a diabetes specialist, per routine care, as defined by American Diabetes Association

guidelines. Any changes in diabetes medication regimen will be documented in the electronic case report form. These data will be used to calculate a medication effect score (MES).

- Participants will be asked to eat nothing after midnight prior to their clinic visits.

8.2 STUDY ASSESSMENTS AND PROCEDURES DEFINITIONS

8.2.1 Informed Consent

See section 10.1.1 for a full description.

8.2.2 Demographics

The following demographic data will be obtained: date of birth/age, gender, child-bearing potential, race, ethnicity.

8.2.3 History & Physical

Medical history deemed clinically significant, relevant to the clinical trial objectives and design, will be collected per body system (allergy/immunology), auditory/ear, blood/bone marrow, cardiac arrhythmia, cardiac general, dermatology/skin), endocrine metabolic, gastrointestinal, hemorrhage/bleeding, hepatobiliary/pancreatic, infection, musculoskeletal/soft tissue, neurologic, ocular/vision, psychiatric, pulmonary/upper respiratory, renal/genitourinary, sexual reproductive function, vascular).

The use of concurrent medications (medications taken within 30 days of screening and during the conduct of the study) will be obtained and documented in source documentation and on the relevant eCRF.

All ongoing medical conditions and adverse events arising from treatment of those conditions present for 30 days or more are generally considered a part of the patient's baseline medical history and must be recorded where indicated.

A full physical examination, including actual measured height (required at screening only) and actual scale measured weight, will be performed by a qualified licensed individual. A review of body systems will include the following:

- Waist circumference
- General appearance, overall well-being and functional capacity
- Skin
- Head, Ears, Eyes, Nose, Throat (HEENT)
- Respiratory
- Cardiovascular
- Abdomen (including liver, gastrointestinal system)
- Musculoskeletal, extremities and mobility
- Neurological
- Vital signs: Assessments of vital signs (e.g., blood pressure, heart rate, temperature) will be performed at all study visits. When possible, blood pressure and heart rate will be determined after the patient has been in the sitting position for 5 minutes. Respiratory rate will only be obtained at baseline (i.e. at the weight management intake visit during screening).

A full physical examination as detailed above will be performed at baseline (weight management screening intake visit), 1-week, 2-weeks, and 1-month post-procedure. Vital signs, including weight, will be taken at all visits with weight management, however, waist circumference will only be measured at the weight management intake visit (screening period), on procedure day, and at the 1-month, 3-month, 6-month, and 12-month post-procedure weight management follow-up visits.

Any abnormalities or changes in intensity, duration or frequency not noted during the initial review of body systems should be documented in the source documentation and reported appropriately in the eCRF. If a new clinically significant finding, or if a change occurs at subsequent visits, the new finding must be assessed for adverse event criteria and will be documented. Resolution of any abnormal findings reported during the study will be noted in the source documentation and the eCRF.

8.2.4 Psychological Evaluation

- **Before** - A psychological evaluation will be completed and scored prior to the first visit. A screening form will be used utilizing inclusion and exclusion criteria to avoid further unnecessary testing. The initial evaluation will be, on average, 1.5 hours.

After - Follow-up visits are usually 1 hour and will largely depend on the plan with the Johns Hopkins Healthful Eating, Activity & Weight Program and the degree to which the participant presents with psychopathology that requires follow-up. Participants will meet with the same study psychologist with whom they did their initial screening 2-4 weeks after the procedure, and develop a follow-up plan which will be adjusted to suit each individual participant's needs. At a minimum, this will include scheduled visits at 1, 3, 6, and 12 months; follow-up visits may be conducted more frequently than specified (i.e. optional 9-month visit) or completed remotely (i.e. telehealth) if clinically indicated—this will be at the discretion of the study psychologists. The participant will follow up with the same psychologist who conducts the initial evaluation, except in urgent or emergency situations in which that psychologist is not available.

8.2.5 Blood, Urine, and Stool Tests

Blood tests including complete blood count, tests of liver and kidney function, serum albumin measurement, electrolytes, urea, creatinine measurements (EUC), and fasting chemistries, including glucose and insulin, will be performed at screening (and again before the procedure if the screening blood tests were done more than 30 days before the procedure) and every study visit thereafter (week 1, week 2, week 4, month 3, month 6, month 12).

A stool occult blood test to identify gastrointestinal bleeding and H. pylori blood antibody test to see if the participant has been exposed to a specific type of bacteria that can cause stomach ulcers will be performed only at screening.

All clinical laboratory assays will be performed at the Johns Hopkins CORE laboratory according to the laboratory's normal procedures. Reference ranges will be supplied by the laboratory and used to assess the laboratory data for clinical significance and out of range pathological changes. Abnormal laboratory values which are unexpected or not explained by the patient's clinical condition should be repeated until confirmed, explained or resolved. Changes from screening will be recorded as an adverse event if clinically significant.

The following clinical laboratory assessments will be completed at specified study visits during the study.

Biochemistry

- Sodium
- Potassium
- Calcium
- Blood Urea Nitrogen
- Creatinine
- Albumin
- Total Protein
- Aspartate transaminase (AST)
- Alanine transaminase (ALT)
- Alkaline phosphatase (ALP)
- Total and indirect bilirubin
- Glucose
- Lactate Dehydrogenase (LDH)
- Insulin
- Pancreatic enzymes: Amylase and Lipase

Coagulation

- Prothrombin Time (PT)
- Partial Thromboplastin Time (PTT)
- International Normalized Ratio (INR)

Hematology

- Hemoglobin
- Hematocrit
- White Blood Cell (WBC) Count
- Platelet Count
- WBC Differential and ANC
- Red Blood Cell (RBC) Count
- Mean corpuscular volume (MCV)

Lipid Profile

- Low-Density Lipoprotein (LDL)
- High-Density Lipoprotein (HDL)
- Triglycerides
- Total Cholesterol
- Total Cholesterol: HDL Ratio
- Non-HDL Cholesterol

8.2.6 Pregnancy Test

A urine or serum beta hCG pregnancy test will be performed on all females of child-bearing potential as a part of the screening process. If the participant is a woman who is able to become pregnant, she will have a repeat pregnancy test on the day of or the day before the embolization procedure. The result of this test must be negative for her to continue in the study. Women of fertile age must agree to use birth control for the duration of the study. Pregnancy tests will also be performed within a week of endoscopies and nuclear medicine gastric emptying tests.

Pregnancy: any report of complications of pregnancy such as miscarriage or congenital abnormality recorded for any female study participant or female partner of a male study participant should be reported immediately as an SAE. Participants will be asked to use contraceptives for the duration of the study, but if they become pregnant during the study, the

participant will be removed from the study. Every effort should be made to gather information regarding the pregnancy outcome until 8 weeks post-partum. It is the responsibility of the Investigator to obtain all pregnancy information.

8.2.7 3D CTA

A 3D CT angiography will be done to check the celiac and gastric vasculature. We plan to embolize only the left gastric and/or gastroepiploic arteries.

8.2.8 Gastric Emptying

Subjects who suffer from diabetes will have a screening gastric emptying (gastric motility/emptying) scan. The result of this scan should be normal for the subject to be able to continue. After the embolization, should any participant present with symptoms of delayed gastric emptying, the PI will order another gastric emptying scan.

8.2.9 Endoscopy with Biopsy

An upper GI endoscopy, also known as esophagogastroduodenoscopy (EGD) will be done to determine any contraindication for the study and to determine the presence of ulceration or any other adverse event (AE).

The endoscopy is also done to determine the health of the GI tract pre- and post-embolization. During the endoscopy, a long, flexible, lighted tube, called an endoscope, is guided through the patient's mouth and throat, then through the esophagus, stomach, and duodenum. A video camera in the endoscope will be utilized to inspect organs and detect abnormalities. Pre-procedure and post-procedure biopsies will be obtained to look at hunger hormone (ghrelin) levels in the stomach. Specifically, the biopsy will be accomplished using a device that looks like a small alligator clip at the end of the endoscope which will close over a very small sample of stomach tissue and allow for its extraction. In the case that an ulcer, inflammation, or mass is noted on endoscopy, additional biopsies may also be taken for further analysis of those regions.

Endoscopic images will be described using standard clinical terms, which include size, location, and depth of observed ulceration. All endoscopy images will be recorded, archived, and reviewed by the same advanced endoscopist.

8.2.10 Quality of Life Questionnaires

A Quality of Life instrument suitable for the general population and patients being treated for obesity will be administered at study visits specified in the schedule of events.

The Impact of Weight on Quality of Life (IWQOL) questionnaire is the first questionnaire developed to specifically assess the effects of obesity on health-related quality of life. The psychometric properties of the IWQOL are excellent, but given its length, a briefer version was developed, the Impact of Weight on Quality of Life-Lite Questionnaire (IWQOL-Lite). The five identified scales (Physical Function, Self-Esteem, Sexual Life, Public Distress, and Work) and the Total score have demonstrated excellent reliability (0.90–0.94 for the scales, 0.96 for Total score), validity, and utility with various groups of obese individuals. In this chapter, the rationale for the development of an obese-specific quality of life measure will be briefly reviewed, followed by the background and development of the IWQOL and IWQOL-Lite (including their psychometric properties), weight loss research using these instruments, and future research directions. It is concluded that the IWQOL-Lite is a reliable, valid instrument that can be utilized in various obese populations, and may be particularly useful as a treatment outcome measure.

8.2.11 Hormone Tests

Fasting levels of obesity-related hormones will also be measured from patient's blood. These will include such hormones as ghrelin, LEAP2, GLP-1, PYY, CCK, leptin, etc.

8.2.13 MRI (with AMRA Profiler)

A semi-automated cloud-based image analysis tool, AMRA Profiler, optimizes MR images to fully analyze entire body compartments, and provide precise body composition measurements. AMRA Profiler uses quantitative fat and water separation to integrate the total fat signal intensity in a compartment of interest; and provide a three-dimensional approach to improve the robustness of the segmentation. This system is quick, cost effective, validated, and reproducible. The automated single scan computes multiple measurements, and is completed in six minutes using fewer coils, no radiation, or contrast. MRI scans with body composition analysis will be performed before the bariatric embolization procedure, and four times over 12 months after the procedure, at weeks 4, and months 3, 6, and 12. A standard 1.5T or 3T scanner with AMRA Profiler will be used to quantify visceral adipose tissue (VAT), abdominal subcutaneous adipose tissue (ASAT), thigh muscle volume, proton-density liver fat fraction, total adipose tissue volume (TAT), total lean tissue volume (TLT), muscle group volumes, intramuscular adipose tissue (IMAT), and individual muscle volumes. The data will be analyzed in conjunction with weight and HbA1c in order to see what patients will be suitable in the future for this procedure to determine which participants are suited and will benefit most from this procedure. As possible characterization of fat will be performed. In addition to the MRI with AMRA Profiler, the scan will also include Siemens work-in-progress sequences for evaluating fatty acid composition. Overall, the MRI is expected to take 30-38 min per session.

8.2.14 Weight Management Counseling

- **Before** – Following consent, the participant will have a total of eight visits over the 2-month screening period with the weight management team at the Johns Hopkins Greenspring Campus Healthful Eating, Activity & Weight Program. This will include an initial 1-hour intake with a physician, consisting of a detailed review of medical history and a physical exam, followed by 7 weekly 15-minute meetings with either a physician as follow-up or other medical staff for weight checks. After their intake visit, reasonable, controlled diet plan will be outlined for the participant. Some visits may occur using a secured telemedicine link (see supplemental form).

After – The first two months after the procedure, participants will have weekly visits with the Johns Hopkins Healthful Eating, Activity & Weight Program (HEAWP), alternating between visiting with a HEAWP physician and a weight check each week. In months 3 to 5, they will have a visit with a HEAWP physician every other week (i.e. two visits a month). In month 6, they will have one visit with a HEAWP physician and one visit with other medical staff at the clinic for a weight check. Lastly, from month 7 to 12, they will only have monthly visits with a HEAWP physician. Each follow-up visit should take around 15 minutes.

8.2.15 Randomization

Data documenting demographic information, medical history, physical examination, medication and prior treatment, clinical labs, pregnancy test, and urinalysis will be reviewed against the eligibility criteria to determine eligibility. The determination will be recorded on the relevant eCRF.

If a patient is determined to be eligible to participate in the study, the patient will be randomized.

Randomization will be determined using assignment by a computer-generated randomization scheme. Upon randomization/enrolment, each patient will be assigned a unique numeric patient identity code.

8.2.16 Bariatric Embolization/Sham Procedure

See section 6.1.1.

8.2.17 CT

Upon completion of the embolization procedure, a CT scan will be acquired to assess bead distribution and fundal coverage.

8.2.18 Assessment of AEs

Patients will be required to report adverse events spontaneously. At every study visit, staff will ask general, open-ended, non-directed questions to obtain information about AEs. If the patient is unable to attend a study visit, AEs can be collected by telephone contact.

At any time during the study, the patient may volunteer information that resembles an AE. The Investigator should obtain all the information required to complete the AE form. Where possible, a diagnosis, rather than a list of signs or symptoms, should be recorded. Any medical management of an event and the resolution of an event must be recorded in source documentation and on the appropriate eCRF using medical terminology according to Sponsor instructions.

The Investigator will assess all AEs for grading, severity and relationship to study treatment(s) and/or procedure(s). Definitions and procedures for assessment can be found in Section 8.3.

8.2.19 Food Logs, Eating Behaviors, and Taste Preferences

- The food log component of our study involves two factors: Lose It! food tracking and the ASA24 questionnaire. The **Lose It! food log** will be used for intervention purposes as well as general data tracking, as participants will be asked to fill it out on a daily basis, while the **ASA24** will be used to obtain more standardized information regarding the subject's eating behavior, and will be conducted over the phone at the specified timepoints in the study calendar.

8.2.20 Hunger Satiety Scale

This scale is a 6-day appetite evaluation that will be collected at the specified timepoints in the study calendar.

8.2.21 HealthReel

The HealthReel app will be used by patients to measure and track changes in their body composition throughout the study.

8.3 ADVERSE EVENTS AND SERIOUS ADVERSE EVENTS

Definition of Adverse Events (AE) and Adverse Device Effects (ADE)

Adverse event (AE) means any untoward medical occurrence, unintended disease or injury, or untoward clinical signs (including abnormal laboratory findings) in subjects, users, or other persons, whether or not related to the investigational medical device.

An adverse device effect (ADE) is an AE, as previously defined, related to the use of an investigational medical device. This includes any adverse event resulting from insufficiencies or inadequacies in the instructions for use, the deployment, the implantation, the installation, the operation, or any malfunction of the investigational device. This includes any event that is a result of a use error or intentional abnormal use of the investigational medical device.

8.3.1 DEFINITION OF SERIOUS ADVERSE EVENTS (SAE) AND SERIOUS ADVERSE DEVICE EFFECTS (SADE)

A serious adverse event (SAE) is an adverse event that:

- a) Led to a death, injury or permanent impairment to a body structure or a body function.
- b) Led to a serious deterioration in health of the subjects, that either resulted in:
 - a. A life-threatening illness or injury, or
 - b. A permanent impairment of a body structure or a body function, or
 - c. In-patient hospitalization or prolongation of existing hospitalization, or
 - d. In medical or surgical intervention to prevent life threatening illness.
- c) Led to fetal distress, fetal death, or a congenital abnormality or birth defect.

Planned hospitalization for a pre-existing condition, or a procedure required by the protocol, without a serious deterioration in health, is not considered a serious adverse event.

A Serious Adverse Device Effect (SADE) is an adverse device effect that has resulted in any of the consequences characteristic of a SAE, as previously defined.

An unanticipated serious adverse device effect (USADE) is a serious adverse device effect, which by its nature, incidence, severity or outcome has not been identified in the current version of the protocol or Investigator's Brochure. This includes unanticipated procedure-related serious adverse events; that is serious adverse events occurring during the study procedure that are unrelated to any malfunction or misuse of the investigational medical device.

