2.3 RISK/BENEFIT ASSESSMENT

2.3.1 KNOWN POTENTIAL RISKS

The prior BEAT Obesity clinical trial allowed for identification of three major areas of risk for bariatric embolization: Gastric Ulcers, Increased Radiation Dose in Obese Participants, and Non Target Vascular Embolization (NTE).

Gastric Ulcers

As was done in the BEAT Obesity Trial, all participants will be treated with gastroprotective agents to mitigate the risks for gastric ulcers. In addition, all participants will be heavily screened to identify and exclude all participants who would be at higher risk for gastric ulcerations.

Currently, arterial embolization with 100-300 μm particles is routinely clinically performed for a number of indications (including embolization of the gastric fundus for control of hemorrhage), and has not been shown to have significant clinical sequelae of tissue necrosis or infarction. In fact, all the investigators in the BEATLES trial have embolized the gastric fundus for gastrointestinal hemorrhages with particles, and have not seen any cases of gastric ulceration/perforation. In the prior BEAT Obesity trial, the procedure was carried out safely with a 300-500 μm embolic, and 8/20 participants had superficial gastric mucosal ulceration seen at 2 weeks, all of which were healed at 3 months. In all reported studies world-wide published at this time, transient superficial mucosal ulcers were commonly observed and none were deemed major complications or major adverse events.

Radiation Dose

The mean radiation dose in the prior BEAT Obesity trial was 5042.6 (± 996) mGy, well below NRC reporting thresholds. There were no radiation associated injuries in any participants observed at follow-up clinic visits. The BEATLES study will use an in-procedure CT scan to serve the same purpose as did the cone beam computed tomography (CBCT) did in the BEAT Obesity Trial, to minimize the risk of NTE and to determine fundal perfusion. The modified fluoroscopic time and software algorithms to reduce radiation exposure developed in the BEAT Obesity Trial will be used in the BEATLES study.

Non Target Vascular Embolization (NTE)

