8.3.5 SERIOUS ADVERSE EFFECT REPORTING

Any SAE, SADE or UADE must be reported by telephone or fax to the Sponsor or its designate as specified in the study procedures within 24 hours of learning of the event. In the event of an emergency, the Investigator will contact the Sponsor safety officer using the coordinates specified in the study procedures manual.

Each AE reported on an SAE form must also be reported in the AE section of the eCRF.

The study investigator shall complete the SAE eCRF and submit to the study sponsor and to the reviewing Institutional Review Board (IRB) as soon as possible, but in no event later than 10 working days after the investigator first learns of the effect. The entire SAE form needs to be completed, if possible, to keep requests for additional information to a minimum. Patients experiencing SAE, SADE or UADE should be followed clinically and with laboratory studies, if appropriate, until medical treatment and/or medical monitoring of the event is no longer required because the event resolves or stabilizes, returns to baseline if a baseline value is available, can

be attributed to agents other than the study treatments or a referral for appropriate follow-up care has been made.

The Principal Investigator, who is also the study sponsor for this study, is responsible for conducting an evaluation of a UADE and shall report the results of such evaluation to the Food and Drug Administration (FDA) in accordance with 21 CFR 812 and to the reviewing IRB within 10 working days after the sponsor first receives notice of the effect. Thereafter, the sponsor shall submit such additional reports concerning the effect as FDA requests.

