8.3.8 REPORTING OF PREGNANCY

Any report of pregnancy or complications of pregnancy such as miscarriage or congenital abnormality recorded for any female study participant or female partner of a male study participant should be reported immediately as an SAE. Participants will be asked to use contraceptives for the duration of the study, but if they become pregnant during the study, the participant will be removed from the study. Every effort should be made to gather information regarding the pregnancy outcome until 8 weeks post-partum. It is the responsibility of the Investigator to obtain all pregnancy information.

Reporting procedures for SAE will be followed as outlined in section 8.3.6.

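### Section 8.3.1(a) sets no severity threshold for injury, and sections 8.2.6, 8.3.1 and 8.3.8 disagree on whether an uncomplicated pregnancy is a serious adverse event

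*Protocol*

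**What the plan says.** Protocol section 8.3.1 defines an SAE by three alternative limbs.

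- Limb (a): the event "Led to a death, injury or permanent impairment to a body structure or a body function".
- Limb (b): the event "Led to a serious deterioration in health of the subjects, that either resulted in" one of four outcomes: life-threatening illness or injury, permanent impairment, hospital admission or a longer stay, or intervention to prevent life-threatening illness.
- Limb (c): the event "Led to fetal distress, fetal death, or a congenital abnormality or birth defect".

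The only carve-out is this: "Planned hospitalization for a pre-existing condition, or a procedure required by the protocol, without a serious deterioration in health, is not considered" an SAE.

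Pregnancy is handled in two further places.

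- Section 8.3.8 covers "Any report of pregnancy or complications of pregnancy such as miscarriage or congenital abnormality recorded for any female study participant or female partner" (meaning a male participant's partner), and has it reported at once as an SAE.
- Section 8.2.6 carries nearly the same sentence but starts from "any report of complications of pregnancy such as miscarriage or congenital abnormality recorded for any female study participant", so an uncomplicated pregnancy is outside it.

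Section 8.3.5 adds: "Each AE reported on an SAE form must also be reported in the AE section of the eCRF". SAP section 3.5 takes total AEs from procedure to 12 months as the primary safety outcome and the total to day 30 as the secondary one.

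**The concern.** A seriousness definition has to separate events needing expedited handling from those that can wait. Under section 8.3.5, SAEs go to the sponsor within 24 hours. Under section 8.3.7 they go to the manufacturer within 24 hours, while non-serious AEs are listed for the manufacturer only at the end of the study. If limb (a) admits every injury, the boundary is lost for the events this procedure is most likely to produce, such as access-site bruising and superficial mucosal lesions. Two assessors could also classify the same haematoma differently, one from (a) and one from (b).

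The same wording carries into device effects. A serious adverse device effect is an adverse device effect with any SAE consequence (8.3.1), and a possible relationship is enough to make an AE a device effect (8.3.2.2).

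For pregnancy, the classification of the same event depends on which section the assessor opens. An event in someone who is not a participant may also be counted in a participant safety total.

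**Working it through.** The documents state no SAE rate, SAE count or pregnancy rate, so there is no figure to reproduce. The check is a reading of the rules against one another.

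**Step 1: does anything limit *injury* in limb (a)?**

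- In (a), *permanent* comes after *injury* and qualifies only *impairment*.
- The carve-out in 8.3.1 concerns planned admissions and protocol procedures, not minor injuries.
- Severity grading does not filter, because section 8.3.2.1 says that severe and serious are not the same thing.
- The AE definition in section 8.3 already includes unintended injury. For injuries, (a) therefore sets the serious bar at the same height as the ordinary AE bar.
- Limb (b) asks for a life-threatening injury. That test adds nothing if (a) has already admitted every injury.

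**Step 2: apply each rule literally to example events.**

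| Event | 8.3.1(a) | 8.3.1(b) | 8.3.1(c) | 8.2.6 | 8.3.8 |
|---|---|---|---|---|---|
| Superficial gastric ulcer, no symptoms, heals | SAE | not SAE | n/a | n/a | n/a |
| Access-site haematoma, resolves | SAE | not SAE | n/a | n/a | n/a |
| Uncomplicated pregnancy, participant | not SAE | not SAE | not SAE | not SAE | SAE |
| Uncomplicated pregnancy, partner | not SAE | not SAE | not SAE | not SAE | SAE |
| Pregnancy with congenital abnormality | depends on case | depends on case | SAE | SAE | SAE |

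The limbs of 8.3.1 are alternatives, so meeting (a) alone is enough. The first two rows show (a) overriding (b). Rows three and four show 8.3.8 standing alone. The last row shows that the pregnancy sections agree once there is a named complication.

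**Step 3: effect on the safety outcomes.** Write total AEs as N = S + M, with S serious and M non-serious.

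- If k minor injuries are classed as serious, the split becomes (S + k) and (M − k). The total is S + k + M − k = N, which is unchanged, because a minor injury was already an AE.
- If p uncomplicated pregnancies are put on SAE forms and then, under 8.3.5, in the AE section of the eCRF, the total becomes N + p. The AE definition in 8.3 extends beyond subjects to other persons, and SAP 3.5 does not say that partner events are left out.

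**Step 4: the cross-reference.** Section 8.3.8 sends the reader to 8.3.6 for SAE reporting procedures. Section 8.3.6 is about informing participants; the SAE procedures are in 8.3.5.

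**The case against.** The best defence has four parts.

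**Limb (a) can be read more narrowly.** An SAE is an AE that *led to* an injury, and a bruise or ulcer is itself the AE. Section 8.3.3 refers to local reactions that do not meet SAE criteria, and section 7.2 keeps participants with medically managed ulcers in the study. Section 2.3.1 says that in published studies "transient superficial mucosal ulcers were commonly observed and none were deemed major complications or major adverse events". All this shows that the authors did not intend minor injuries to be serious. It stands as evidence of intent, though *major* there is not the same scale as *serious* in 8.3.1. It does not repair (a): two available readings are the reason to fix the wording.

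**The pregnancy rule may be only a route.** Section 8.3.8 says *reported as an SAE*, which could mean that pregnancies follow the SAE channel without being SAEs. An uncomplicated pregnancy is also not clearly an untoward occurrence under 8.3, so its entry in the AE eCRF is possible, not certain. Both points stand. The pregnancy issue is therefore a contradiction to resolve, not a settled rule.

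**No safety endpoint or halting rule uses an SAE count.** This stands. The outcomes are total AEs, and the halting events in section 7.1 are named events.

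**Stronger claims go too far.** A reader might infer that SAEs would be inflated mainly in the bariatric embolization (BAE) arm, because only that arm has catheterisation and embolization (6.1.1). For procedural injuries that is plausible, but neither document states or quantifies it. All participants receive lidocaine and a skin nick, blood draws, and endoscopy with biopsy, and pregnancy has no arm-specific mechanism. A reader might also multiply the prior trial's ulcer rate, 8/20 = 40%, by 27 to get 10.8 spurious SAE patients. Those ulcers were seen at 2 weeks with 300-500 µm beads and had healed by 3 months. Routine post-procedure endoscopy here is at 3 months and the beads are 100-200 µm, so the figure does not transfer.

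**Conclusion.** The concern holds as two faults in the safety-reporting rules.

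1. Read literally, 8.3.1(a) makes a minor injury serious and leaves (b) without force for injuries. The reach of this fault is the serious/non-serious split, the device-effect classification built on it, and the 24-hour reports. The total-AE outcomes at 12 months and day 30 are unaffected.
2. Sections 8.2.6, 8.3.1(c) and 8.3.8 contradict one another on uncomplicated pregnancy. This is the only route by which a safety outcome could change: each such pregnancy entered as an AE adds one event to the total, and a partner's would be an event in a non-participant.

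No number of affected events is claimed, since any minor-injury or pregnancy rate would be an assumption from outside the documents, and no imbalance between arms is claimed. The conclusion assumes that assessors apply the text as written and, for the AE total, that an event put on an SAE form is coded as an AE as 8.3.5 directs. If 8.3.8 is meant only as a reporting route, the effect on the total disappears, but the text still has to say so.

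**What to change.** - **Section 8.3.1(a):** qualify the word, for example *serious injury*, or delete it so that limb (b) governs injuries.
- **Sections 8.2.6, 8.3.1 and 8.3.8:** reconcile them. State whether an uncomplicated pregnancy is an SAE or only follows the SAE reporting route. Either way, keep prompt reporting of every pregnancy, so that the sponsor and manufacturer are not told later than now.
- **Section 8.3.8:** correct the cross-reference from 8.3.6 to 8.3.5.
- **SAP sections 3.5 and 5.4:** add a sentence that partner pregnancies are listed separately and not counted in participant AE totals.

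The cost is a protocol amendment of a few words in three sections and one SAP sentence. No new participant data are needed. If pregnancies are to be reported promptly but not coded as SAEs, the eCRF needs a separate form or flag. If events have already been classified under the present wording, the blinded team should check their seriousness coding once against the revised text.
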